Diabetic nephropathy accounts for the majority of chronic kidney disease. In Japan, it has been the main primary disease leading to the introduction of maintenance dialysis (hemodialysis, peritoneal dialysis) since 1998²⁾ and accounted for 43.7% of the total number of patients on dialysis in 2015.³⁾ In Japan, the total costs of artificial dialysis are around 1.4 trillion yen (2009),⁴⁾ meaning that dialysis accounts for 4% of Japan's total health care costs. Controlling the number of patients who receive dialysis is therefore a significant societal issue. Patients receiving dialysis face many employment and lifestyle restrictions, and the burden on their caregivers (e.g., families) is also considerable. In addition, the five-year survival rate of patients who have been started on dialysis has been reported to be 60.8%.³⁾ Thus, it is important for patients with diabetes to diagnose and treat nephropathy early to inhibit its progression from the viewpoint of the prognosis of patients, the quality of life of patients and caregivers, and health economics. In early (Stage 2) nephropathy, in which the urine albumin level is 30 mg/gCr or above, if treatment is not administered, the urine albumin level will rise at a rate of around 10 to 20% a year until after 10 to 15 years the patient has progressed to overt (Stage 3) nephropathy. The patient's glomerular filtration rate (GFR) will then gradually decrease (by between 2 and 20 mL/min/1.73 m² per year), ultimately resulting in end-stage renal failure (renal failure stage, dialysis therapy stage).⁵⁾ It has been reported that as the urine albumin level increases, the incidence of cardiovascular events increases,^{2,6)} and the prognosis for renal function worsens.⁷⁾ Thus, treatment guidelines recommend starting treatment in the early stage, i.e., early nephropathy stage. In addition, it has been reported that improving blood pressure management even in the overt nephropathy stage can result in remission from macroalbuminuria to normal urine albumin levels, and intensive therapy therefore is believed to be critical for patients with overt nephropathy as well.^{8,9)}

At present, the only drugs that are indicated for diabetic nephropathy in Japan are losartan potassium, an ARB drug the use of which is limited to type 2 diabetes patients with hypertension and proteinuria (urine ACR \geq 300 mg/g), and imidapril hydrochloride, and ACE-I drug the use of which is limited to type 1 diabetes patients.

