(2) Name and Description of Investigational Product

TA-7284 (nonproprietary name: canagliflozin hydrate) is a sodium glucose co-transporter (SGLT) 2 inhibitor for which Mitsubishi Tanabe Pharma Corporation obtained marketing approval in Japan in July 2014 for an indication for type 2 diabetes for Canaglu 100 mg Tablets.

[REDACTED]

[REDACTED]

[REDACTED]

SGLT2 is distributed in the renal tubules and is involved in the reabsorption of around 90% of the glucose that is filtered from the blood by the glomerulus and that subsequently passes into the glomerular filtrate. SGLT2 inhibitors selectively inhibit SGLT2 and thereby inhibit urinary glucose reabsorption, normalizing blood glucose levels. It appears that SGLT2 inhibitors, by effecting a correction in the hyperglycemic state, will alleviate “glucose toxicity” and help to inhibit the progression of diabetes and/or help to prevent the emergence and progression of complications.

In addition, independent of its blood glucose lowering effects, which result from its increasing of urinary glucose excretion, TA-7284 appears to also act to reduce intraglomerular pressure via an intrarenal mechanism (the promotion of tubuloglomerular feedback [a mechanism in which both glomerular filtration and Na^+ and body fluid renal tubule reabsorption are involved]) that results in a rapid and slight reduction in the estimated glomerular filtration rate, and thus results in a decrease in hyperfiltration and albuminuria. TA-7284 therefore inhibits the progression of diabetic nephropathy by effects that are different from those of ACE-I and ARB drugs, and it is therefore expected that this mechanism will be additive to the renal protective effects of ACE-I and ARB drugs. Figure 1.1 shows the hypothesized mechanism of renal protection of ACE-I and ARB drugs as well as the hypothesized mechanism of pharmacological action for TA-7284.

Figure 1.1: Hypothesized Mechanism of Pharmacological Action of TA-7284

As shown above, TA-7284's inhibition of SGLT2 increases glomerular afferent arteriole tonus and thereby reduces intraglomerular pressure, and therefore appears to result in a

hemodynamically mediated reduction in intraglomerular pressure that is reflected in a sudden, slight decrease in the GFR. It appears possible that the reduction in intraglomerular pressure inhibits the progression of diabetic nephropathy through the reduction in urine albumin levels that is seen in treatment with TA-7284.

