The change in the eGFR when TA-7284 was administered in combination with metformin for 104 weeks was investigated in the CANTASA-SU study (study [REDACTED]) in type 2 diabetes patients, in which glimepiride was used as the control. Although the TA-7284 group exhibited a transient decrease in the eGFR immediately after administration, a constant eGFR level was subsequently maintained, and the change in the eGFR from baseline was -2.7 ml/min/1.73 m² (95% confidence interval, -3.5 to -1.9) in the TA-7284 100 mg group and -3.9 ml/min/1.73 m² (95% confidence interval, -4.7 to -3.0) in the TA-7284 300 mg group. In the glimepiride group, on the other hand, the eGFR decreased at a constant rate after the start of the study, and the change in the eGFR from baseline was -5.4 ml/min/1.73 m² (95% confidence interval, -6.2 to -4.5). These results suggested that the long-term use of TA-7284 may inhibit the reduction in the eGFR compared to patients receiving glimepiride, in whom the eGFR continues to fall at a constant rate.

Safety

There are at present no results from clinical studies in patients with Stage 3 diabetic nephropathy (overt nephropathy). The results of Japanese clinical pharmacology studies conducted in type 2 diabetes patients with moderate renal impairment and Japanese clinical studies in type 2 diabetes patients are described below.

In a Japanese phase 2 dose-finding study and phase 3 studies that were conducted in type 2 diabetes patients, 953 adverse reactions (including clinical laboratory abnormalities) were reported in 474 of 1629 subjects (29.1%). The most common adverse reactions included asymptomatic hypoglycemia, hypoglycemia, pollakiuria, increased blood ketone bodies, and constipation. The package insert lists the following as "clinically significant adverse reactions": hypoglycemia, dehydration, ketoacidosis, septicemia, and pyelonephritis. In addition, the following are listed as "other adverse reactions" that occur in at least 1% of patients: constipation, thirst, cystitis, pollakiuria, vulvovaginal candidiasis, ketosis, asymptomatic hypoglycemia, and increased blood ketone bodies.

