5.1. Efficacy Analysis Sets

(1) Efficacy Analysis Sets

1) FAS

The analysis sets consisting of all randomized subjects other than the following constitute the FAS.

- Subjects who were not type 2 diabetes mellitus patients with Stage 3 diabetic nephropathy (overt nephropathy)
- All subjects who did not take the investigational product at all
- All subjects for which no post-randomization efficacy data are available

2) PPS

The PPS is the FAS, minus the following subjects.

- Subjects who have deviated from the inclusion criteria
- Subjects who have met the exclusion criteria
- Subjects who have violated the stipulations about the prohibited concomitant drugs
- Subjects with a rate of compliance with the investigational product of 75% or lower
- Subjects with treatment periods shorter than 52 weeks

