6.2.1. Tabulation by eGFR Assessment Time Point

When tabulating the eGFR at each assessment time point, data that fall within the allowable time windows defined in “Table 6.2: Test/Observation Schedule Allowable Time Windows” will be used. For data that have been reported as having been collected at treatment period discontinuation, data that were collected within the allowable time window for the day of treatment period discontinuation will be used. Although a data tabulation at discontinuation will not be performed, data that have been collected within the allowable time window for the day of treatment period discontinuation that are also within the allowable time window for the time point in question will as a rule be used as data for that time point. In addition, if multiple measurements have been taken within an allowable time window, data from the test that was performed on the day closest to the target day will be used. If there are multiple measurements, and the difference in the numbers of days between the day of each measurement and the target day are the same, then the data that were collected earlier will be used.

6.2.2. Tabulation of the eGFR at Each Assessment Time Point When Imputing Data Outside the Allowable Time Window

When tabulating the eGFR data for each assessment time point, the data stipulated in 6.2.1 will be combined with data imputed by means of multiple imputation (██████████) for data for which the assessment time point was outside the allowable time window. A linear regression model with the data at each assessment time point from the first day of the treatment period until Week 88 of the treatment period as the explanatory variable will be used to replace missing values for each assessment time point from Week 4 of the treatment period through Week 104 of the treatment period. It will be assumed that the pattern of missing values is non-monotonic.

6.2.3. Tabulation of Endpoints Other Than the eGFR and Urine ACR at Each Assessment Time Point

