7.6. Analysis of Efficacy

7.6.1. Primary Endpoints

7.6.1.1. Primary Analysis

Analysis population(s): FAS, PPS

Analysis parameter(s): Proportion of subjects with a decline of 30% in the eGFR at Week 104 of the treatment period

Analysis method:

In accordance with “6.2.2. Tabulation of the eGFR at Each Assessment Time Point When Imputing Data Outside the Allowable Time Window,” a dataset will be prepared using [REDACTED]. The estimated values from this dataset, and the variance thereof, will be combined using Rubin’s rule, and the proportion of subjects with a decline of 30% in the eGFR at Week 104 of the treatment period, and the 95% confidence interval thereof, will be shown for each treatment group. The point estimate for the difference between the groups (placebo group minus TA-7284 group) and the 95% confidence interval according to the Farrington-Manning method will also be shown.

Listings

Analysis population(s): Randomized subjects

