7.6.1.2. Secondary Analysis

Analysis population(s): FAS, PPS

Analysis parameter(s): Proportion of subjects with a decline of 30% in the eGFR at Week 104 of the treatment period

Analysis method:

In accordance with “6.2.2. Tabulation of the eGFR at Each Assessment Time Point When Imputing Data Outside the Allowable Time Window,” a dataset will be prepared using [REDACTED]. The estimated values from this dataset, and the variance thereof, will be combined using Rubin’s rule, and the proportion of subjects with a decline of 30% in the eGFR at Week 104 of the treatment period, and the 95% confidence interval thereof, will be shown for each treatment group.

In addition, for each of these datasets, a logistic regression model will be applied with a decline of 30% in the eGFR at Week 104 of the treatment period as the target variable, treatment group and the stratification factor eGFR on the first day of the run-in period (≥ 30 and < 45 , ≥ 45 and < 60 , ≥ 60 and < 90) as factors, and the urine ACR (first morning void urine) as covariates, and the estimates and variances thereof will be calculated and combined in accordance with Rubin’s rule. An intergroup comparison of these results will be performed, and the odds ratio of a 30% decline in the eGFR in the TA-7284 group relative to the placebo group at Week 104 of the treatment period, and the 95% confidence interval thereof, will be presented.

Listings

Analysis population(s): Randomized subjects

7.6.1.3. Other Analysis 1

Analysis population(s): FAS, PPS

Analysis parameter(s): Proportion of subjects with a decline of 30% in the eGFR at Week 104 of the treatment period

Analysis method:

The proportion of subjects with a 30% decline in the eGFR at Week 104 of the treatment period, and the 95% confidence interval thereof, will be presented for each treatment group for the dataset obtained through the replacement of missing values at Week 104 of the treatment period in accordance with “6.3 Handling of eGFR Data at the End of the Treatment Period.” The point estimate for the difference between the groups (placebo group minus TA-7284 group) and the 95% confidence interval according to the Farrington-Manning method will also be shown.

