Endpoints Other Than the eGFR and Urine ACR at Each Assessment Time Point,” each of the mean changes at each assessment time point from Week 4 to Week 104 in the eGFR, HbA1c, fasting glucose, blood pressure (systolic blood pressure, diastolic blood pressure), lipids (HDL-C, fasting neutral lipids), and body weight, and the mean percent changes at each assessment time point from Week 4 to Week 104 in the eGFR, lipids (HDL-C, fasting neutral lipids), and body weight will be analyzed in a mixed model for repeated measures using a restricted maximum likelihood (REML) approach, with treatment group, assessment time point, treatment group—assessment time point interaction, and the stratification factor of the eGFR on the first day of the run-in period (≥ 30 and < 45 , ≥ 45 and < 60 , ≥ 60 and < 90) as factors, and the values of the assessment parameters on the first day of the treatment period and the interactions between the assessment time points and the values of the assessment parameters on the first day of the treatment period as covariates. The LS means and standard errors at each measurement time point for each treatment group will be presented. The differences between the groups in the LS mean (the TA-7284 group minus the placebo group) and the 95% confidence intervals and P values will also be presented. In addition, time profiles will be prepared for each treatment group for each of the mean change and the mean percent change, with the LS means and standard errors, calculated based on MMRM, along the y-axis and each measurement time point up through Week 104 along the x-axis.

The Kenward-Roger method will be used to adjust the degrees of freedom, and an unstructured covariance structure will be used for within-subject error modeling.

However, in within-subject error modeling, if the model fails to converge when using an unstructured covariance matrix, the covariance matrix will be changed according to the following procedure, and the first covariance matrix with successful convergence will be used to perform the analysis.

Heterogeneous Toeplitz (TOEPH) → Heterogeneous AR(1) (ARH(1)) → Heterogeneous CS (CSH) → Toeplitz (TOEP) → First-order autoregressive (AR(1)) → Compound symmetry (CS)

Listings

Analysis population(s): Randomized subjects

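### The readable imputation model for the primary endpoint does not list treatment group; if imputation is pooled over arms, the Week 104 risk difference is biased in a direction set by how the effect evolves

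*SAP*

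**What the plan says.** SAP 6.2.2 gives the imputation model for eGFR: "A linear regression model with the data at each assessment time point from the first day of the treatment period until Week 88" supplies the explanatory variables, missing values from Week 4 to Week 104 are the targets, and the missing-data pattern is taken as non-monotonic. The name of the procedure is blacked out there and in SAP 7.6.1.1, 7.6.1.2 and 7.6.3.8. The appendices are redacted as well.

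SAP 7.6.1.1 builds the primary risk difference (placebo minus TA-7284, Farrington-Manning interval) on these data: "The estimated values from this dataset, and the variance thereof, will be combined using" Rubin's rule. The adjusted odds ratio (7.6.1.2) and the 40% endpoint (7.6.2.1) use the same data. Protocol 13.3.2 says only that multiple imputation will be used.

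Other models do name treatment. The logistic model has "treatment group and the stratification factor eGFR on the first day of the run-in period" as factors. The eGFR model in SAP 7.6.2.3 "will be analyzed in a mixed model for repeated measures using a restricted maximum likelihood (REML) approach, with treatment group, assessment time point" and their interaction. SAP 7.6.3.8 says that imputation for subgroups is done by subgroup. No readable sentence says by treatment group.

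**The concern.** Under Protocol 12.2 and Table 5.1, stopping treatment starts a 4-week follow-up, after which the subject is finished. Nearly every early stopper therefore has an imputed Week 104 value, and so an imputed primary outcome.

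The protocol expects the arms to follow different courses. Section 1 (2) says that the drug "results in a rapid and slight reduction in the estimated glomerular filtration rate". Section 1 (3) reports, from a 104-week study against glimepiride in a different population, that "Although the TA-7284 group exhibited a transient decrease in the eGFR immediately after administration, a constant eGFR level was subsequently maintained", while the comparator fell steadily. A regression fitted to both arms without a treatment term gives the missing values of both arms one blended course after the last observed visit. The subject's own earlier values carry part of the arm difference, but not all of it. An early dip on drug can also be read by the pooled model as the start of a steep decline.

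At stake are the primary estimate in the FAS, the adjusted odds ratio and the 40% endpoint.

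**Working it through.** **Plan figures.** There is no result to reproduce. The sample size is 300 (150 per group), but its rationale is not readable in the public copy. The documents give no dropout rate and no dip size for this population. For slope they say only that the "glomerular filtration rate (GFR) will then gradually decrease (by between 2 and 20" mL/min/1.73 m² per year.

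**Inputs from the documents.** Visits follow Protocol 9.2.3.1: Day 1, every 4 weeks to Week 52, then Weeks 64, 76, 88 and 104. Baseline is the mean of the run-in and Day 1 values. The event is a fall of at least 30% at Week 104. The glimepiride study gives changes of −5.4 (comparator) and −2.7 (100 mg) over 104 weeks. One scenario uses them as −5.4/2 = −2.7 per year against a 2.7-unit dip and then no change.

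**Assumed inputs.** Baseline eGFR mean 55, SD 15, limited to 30–90; slope SD 4.5 per year; within-person CV 7%; dropout uniform over 104 weeks, equal by arm and unrelated to eGFR.

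**Method.** 150,000 subjects per arm, with sequential regression imputation run three ways: pooled, with a treatment covariate, and by arm. Risk difference in percentage points, full data → pooled; loss = (full − pooled)/full:

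| Placebo vs drug (per year; dip) | 10% dropout | 20% dropout |
|---|---|---|
| −6 vs −3; none | 17.9 → 17.1 (4%) | 17.7 → 16.3 (8%) |
| −6 vs −2.5; 2 | 15.3 → 14.4 (6%) | 15.4 → 13.5 (12%) |
| −6 vs −3; 3 | 9.9 → 9.0 (9%) | 9.8 → 7.9 (19%) |
| −6 vs flat; 2.7 | 24.0 → 22.8 (5%) | 24.0 → 21.3 (11%) |
| −2.7 vs flat; 2.7 | 5.0 → 4.6 (8%) | 5.2 → 4.3 (17%) |
| −4 vs −2; 2 | 4.9 → 4.5 (8%) | 5.0 → 4.0 (20%) |
| −10 vs −5; 2 | 30.0 → 28.4 (5%) | 29.8 → 26.6 (11%) |
| −10 vs −5; 3 | 26.3 → 24.8 (6%) | 26.5 → 23.4 (12%) |

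The treatment covariate stays within 0.15 points of full data, and by-arm imputation within 0.3.

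**Where the loss arises.** When dropout is unrelated to eGFR, pooled estimate = (1 − m) × full + m × contrast among the imputed, where m is the missing share. In the second row at 20%: 13.5 = 0.8 × 15.4 + 0.2x, so x = (13.5 − 12.32)/0.2 ≈ 6. The imputed subjects contribute a contrast of about 6 points instead of 15. The same sum gives about 11 instead of 18 with no dip, and about 0 instead of 10 with a 3-unit dip.

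**Timing.** At 20% dropout the loss is 2–8% if all of it falls after Week 88, and 17–32% if all of it falls in the first 24 weeks.

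**Shape of the effect, 20% dropout.** With −6 per year against −1 in year 1 and −6 thereafter: 15.3 → 15.2. With −6 against 0 in year 1 and −8 thereafter: 12.7 → 13.4, an overstatement. A second set of runs (slope SD 5 per year, residual SD 4, same baseline) gave the same picture: 16.1 → 15.6 for a year-1-only effect and 15.2 → 16.0 for an early gain that fades. The treatment covariate gave 16.4 and 15.2.

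**Other dropout patterns.** In that second set, with a persisting effect, unequal dropout (25% vs 10%) gave 13.9 → 11.6, and dropout depending on observed eGFR gave 13.6 → 11.1.

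**No effect at any visit, 20% dropout, 150 per arm.** The mean difference is 0.0 with or without the covariate; rejection is 2.8% pooled and 3.7% with the covariate.

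**The case against.** The strongest objection is redaction. The method term is blacked out wherever this imputation is specified, and text removed that way is not missing from the plan. A reader might infer that the SAP does pool the arms. The documents do not support that, since even a complete variable list would be compatible with fitting by arm. What stands is narrower: the readable sentence names the model type and its explanatory variables without treatment, and nothing readable supplies it.

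A reader might also infer that any such bias must be conservative. It need not be. The direction depends on an effect that keeps growing to Week 104, and the protocol's support for that profile comes partly from another population.

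The plan has useful cross-checks. SAP 7.6.1.4 estimates the same risk difference from in-window data without imputation. Under dropout that is equal by arm and unrelated to eGFR it came within 0.2 points of full data. The eGFR repeated-measures model in 7.6.2.3 gives Week 104 contrasts with treatment in the model. The PPS, which drops "Subjects with treatment periods shorter than 52 weeks", loses less (2–6% at 20% dropout). All of this stands, but none of it corrects the FAS primary estimate, the odds ratio or the 40% endpoint.

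Finally, the target matters. If imputed values are meant to represent the course off drug, the pooled result at 20% dropout is close with no dip (16.3 vs 16.1) but low with a 2-unit dip (13.5 vs 14.5) or a 3-unit dip (7.9 vs 9.7).

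**Conclusion.** The concern holds conditionally. If imputation is pooled over arms, the primary risk difference under continued treatment is biased. With a persisting effect and dropout spread over the study, the loss is about 4–9% of the difference at 10% dropout (0.4–1.6 points) and 8–20% at 20% (0.9–3.2 points), beside a sampling SD of about 5 points at 150 per arm. These figures are for true differences of about 5 to 30 points. When the true difference is small the relative loss is larger: 3.0 → 1.5 at 20% dropout in the second set of runs (−5 vs −3 per year, 3-unit dip). The bias is about nil for a year-1-only effect and reverses if an early gain wanes. Slopes, dip, variances and dropout are all assumptions.

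The absence of bias under the null means no effect at any visit. Two arms that merely happen to meet at Week 104 by different courses can still be pulled apart: a 5-unit dip with −6 vs −3.5 per year gave −0.1 → −1.9 at 20% dropout, against the drug.

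A reader might infer a definite loss of power. At 20% dropout with a 2-unit dip, the chance that the 95% interval excludes zero was 74% pooled against 84% with the covariate (Wald interval in place of Farrington-Manning). But the readable text sets no such success rule, and the figures inherit every assumption above. Nor do the null runs suggest a raised false-positive rate.

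The point is worth fixing because the repair is cheap and works for every effect shape tried.

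**What to change.** First confirm the full imputation model against the unredacted SAP. If it already includes treatment or runs by arm, nothing changes. If not, state in SAP 6.2.2, before database lock, that treatment group is an explanatory variable in the imputation model, or that imputation is done by treatment group. Apply this in 7.6.1.1, 7.6.1.2, 7.6.2.1 and 7.6.3.8, and record it as Protocol 13.4 requires. After lock, the same section allows a documented added analysis, kept distinct from the planned ones.

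The cost is a sentence or two, one added term, and a slightly noisier estimate. At 150 per arm and 20% dropout the SD is 4.9 against 4.7 points (2-unit dip) or 5.2 against 5.0 (3-unit dip), with practically the same interval width.

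Two additions are optional. One is to prefer the covariate form in small subgroups, where by-arm fitting puts 17 predictors on about 40 complete subjects. The two forms performed alike at 50 per arm (SD 8.5 covariate, 8.4 by arm), so this is a matter of taste. The other is a line saying whether imputed Week 104 values represent continued treatment.
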